11. DATA

11.1. DATABASES

For each database used to enter data, please describe the database into which data will be entered (i.e., nFORM and/or other databases), including both performance measure data you plan to use in your local evaluation and any additional local evaluation data. Describe the process for data entry (i.e., who will enter the data into the database).

Database Name	Data Entered	Process for Data Entry
nFORM	Performance Measurement Data	Entered directly by participants, and by program staff

Qualtrics	Local evaluation data, participant outcomes (OLLE survey)	Entered directly by participants, and by MER evaluation staff
-----------	---	---

* you may add rows by hitting the tab button, or right click and select insert row below

11.2. DATA REPORTING AND TRANSFER

For each database provided in the table above, please indicate the ability to export individual-level reports to an Excel or comma-delimited format and whether identifying information is available for linking to data from other sources.

Database Name	Ability to Export Individual Reports?	What identifying information is available to facilitate linking to other data sources?
nFORM	Yes	nFORM Client ID, Name, DOB
Qualtrics	Yes	nFORM Client ID, Name, DOB

* you may add rows by hitting the tab button, or right click and select insert row below

11.3. CURRENT SECURITY AND CONFIDENTIALITY STANDARDS

For each database provided in Section 11.1, please Indicate the ability to be able to encrypt data access during transit (for example, accessed through an HTTPS connection); be able to encrypt data at rest (that is, when not in transit), have in place a data backup and recovery plan; require all users to have logins and passwords to access the data they are authorized to view; and have current anti- virus software installed to detect and address malware, such as viruses and worms.

Database Name	Ability to encrypt data during transit?	Ability to encrypt at rest?	Data Backup and Recovery Plan?	Require all users to have logins and passwords?	Current Anti-Virus Software Installed?
Qualtrics	Yes	Yes	Yes	Yes	Yes

* you may add rows by hitting the tab button, or right click and select insert row below

**Statistical Analysis Plan**

**1/16/2025**

## 1. Data Analysis

*Briefly describe the planned approach for data analysis. If an impact analysis is proposed, name the key dependent and independent variables, and describe any methods to minimize Type I error (i.e., finding positive impacts by chance) such as limiting the number of impacts to be analyzed and/or multiple comparison correction. Describe proposed approach(es) for addressing missing data.*

### Identify study sample

The study sample includes participants who: 1) gave recorded informed consent to be part of the study, and 2) took both an entrance and exit survey (for attitudinal outcomes) or entrance and follow-up survey (for behavioral outcomes). The CONSORT diagram in Appendix C shows exclusion criteria and the anticipated size of the overall study sample. The analytic sample for particular outcome measures will vary based on missing data.

### Defining analysis measures

For each outcome construct, we have identified the relevant measures from nFORM that are theoretically aligned with that construct. We will generate a correlation matrix between items in a given construct to ensure that theoretically related items are also empirically related in our data set. Items that are not strongly correlated with other items in a construct will be removed as necessary. Factor analysis will be used to ensure that all construct items hang together (using an alpha of 0.7 or higher as the threshold). If an alpha of 0.7 cannot be obtained, that outcome will be removed.

Once we are confident that all of the items align with a given construct, we will create a composite measure by taking an average of the scores on each non-missing item in the construct. The measure definition matrix below provides information on each proposed outcome. For composite measures, a change score will be calculated between a participant's pre-program composite score and post-program composite score. For standalone survey items, a change score will be calculated between a participant's pre-survey and post-survey responses.

For the sake of consistency and simplicity, parenting and co-parenting analyses will use a participant's youngest child as the focal child.

Measure	Sample	Variable Type	Data source(s)	Variable Name	Definition
Parenting attitudes	Has at least one child age 24 or younger, saw child within past month	Continuous (range from 1 to 5 where 1 is strongly disagree and 5 is strongly agree)	nFORM entrance, nFORM exit	Par_Att	Average of 7 survey items that relate to frequency of key parenting attitudes.

Parenting behaviors	Has at least one child age 24 or younger, saw child within past month	Continuous (range from 1 to 5 where 1 is never and 5 is every day or almost every day)	nFORM entrance, OLLE 1-year follow-up	Par_Beh	Average of 7 survey items that relate to frequency of positive interactions with participant's youngest child.
Co-parenting behaviors	Has at least one child age 24 or younger	Continuous (range from 1 to 5 where 1 is strongly disagree and 5 is strongly agree)	nFORM entrance, OLLE 1-year follow-up	Copar_Beh	Average of 11 survey items that relate to positive interactions with the mother of participant's youngest child.
Financial behaviors	Has at least one child age 24 or younger	Dichotomous (0/1)	nFORM entrance, OLLE 1-year follow-up	Fin_Beh	Binary measure of having opened a checking/savings account.
Financial attitudes	All study participants	Continuous (range from 1 to 5 where 1 is strongly disagree and 5 is strongly agree)	nFORM entrance, nFORM exit	Fin_Att	Average of 4 survey items that relate to levels of agreement with key financial attitudes.
Employment behavior	All study participants who came into the program without a resume	Dichotomous (0/1)	nFORM entrance, OLLE 1-year follow-up	Emp_Beh	Binary measure of having a completed resume to give employers.
Employment attitudes	All study participants	Categorical (range from 1 to 5 where 1 is never and 5 is always)	nFORM entrance, nFORM exit	Emp_Att	Average of 4 survey items that relate to levels of agreement with key employment attitudes.

**Commented [A1]:** Shouldn't this be OLLE 1-year follow-up? Same for employment behavior below.

**Commented [A2R1]:** Yes!

**Commented [A3]:** Also, FYI, I updated the year for the plan updated date in the headers.

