1. PROGRAM SUMMARY

Please provide a brief summary of your grant project including the needs to be addressed, the services provided, and the population served.

The Fresno region of California, at both the city and county levels, is a region impacted by high rates of poverty and unemployment. Prior research suggests that poverty is often inextricably linked to high crime rates. High crime rates can then lead to high rates of incarceration, thereby contributing to chronic father absenteeism and the breakdown of healthy families. The purpose of the Fresno Fatherhood program is to employ a comprehensive and holistic healthy marriage, responsible parenting and economic stability education and related services to at-risk adult community fathers (i.e., 18 and older) who have children aged 24 years or younger and reside in areas of high poverty. While the program does not plan on serving only fathers who are housed in treatment facilities, non-custodial, or justice involved, the grantee (FAWIC) expects that many will have these characteristics.

The core services of Fresno Fatherhood include: healthy marriage, responsible parenting, and economic stability education and services. These services will be delivered by using a primary workshop focused on fatherhood skills using the National Fatherhood Initiative's 24/7 Dad evidence-based/evidence-informed curricula; job readiness services, including career exploration and planning; job-driven employment services, including development of skills tied to demand jobs in growth sectors of the local economy; job placement assistance; intensive case management and service navigation support; mentoring to encourage and support fathers in applying the knowledge and skills they acquire through the project; supplemental workshops focused on life skills, financial literacy and personal development; and referrals to a full array of support services through both grant-funded and leveraged resources. FAWIC will provide parenting and relationship instruction via a primary workshop to 63 fathers in year 1 and 125 annually in years 2-5.

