8. SAMPLE

8.1. TARGET POPULATION(S)

For each target population identified in Section 1.2, please describe the target population(s), and explicitly state whether the population(s) differs from those who will be broadly served by the grant. Describe how the target population will be identified. Explicitly state the unit of analysis (e.g., non-residential father, unmarried couple).

Description of Target Population	How is the population different from those who will be broadly served by the grant?	How will the target population be identified?	Unit of Analysis
Target population is community fathers (ages 18 and older), who have children ages 24 and younger and reside in communities with high rates of poverty.	No difference, all program participants will be study participants.	The sample will be identified and recruited by community partner referrals and program staff.	Community adult fathers

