#### Handling missing data

##### Outcomes

When creating the composite measures for our behavior and attitude outcomes, we will create a composite score by taking the average of multiple individual items. For these measures, our current plan is to use 20% as a threshold for allowable missing items, based on guidance from evaluation technical assistance resources. This plan is contingent on the final distribution of missing data in our data set. If participants have more than 20% of items missing for a given construct, the respondent will be assigned a missing value for that construct and will be excluded from the analytic sample for that outcome. We will not be imputing truly missing values for outcomes. To create a construct score, the average will divide by the number of non-missing values in the construct.

Participants who have not seen their child within the past month will have their parenting behavior responses set to “Never” (1) and will be included in the analytic sample for that outcome.

Data for the implementation outcomes could be missing as a result of programmatic data entry issues. For the sake of this evaluation, we assume that any primary or support services received by a participant are being accurately logged into nFORM, so a lack of documented attendance, service contacts, referrals, etc. is indicative of lack of services (i.e., a participant not receiving the program components as intended).

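### The parenting-attitudes analysis (R1) is limited to fathers with recent child contact, at an unstated survey wave, although R1 is posed for all participating fathers

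*SAP*

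**What the plan says.** R1 (Protocol 1.1 and 1.2) asks whether program participants improve in parenting attitudes from entrance to program completion. Protocol 8.1 defines the population: "Target population is community fathers (ages 18 and older), who have children ages 24 and younger and reside in communities" with high poverty. It says of the difference between the study population and those served: "No difference, all program participants will be study participants". Neither statement mentions recent contact with a child.

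The SAP's general rule (Identify study sample) is similarly broad. A participant must have consented and "took both an entrance and exit survey (for attitudinal outcomes"). It adds that analytic samples will differ between outcomes because of missing data.

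The measure matrix (Defining analysis measures) is narrower. The sample cell for Par_Att reads "Has at least one child age 24 or younger, saw child within past month". The parenting-behavior row carries the same cell. The co-parenting row requires an eligible child but no contact.

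One rule brings fathers without contact back in (Handling missing data, Outcomes): "Participants who have not seen their child within the past month will have their parenting behavior responses set to" the lowest score, and they stay in the sample for that outcome. There is no corresponding rule for attitudes.

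**The concern.** The restriction is not explained and does not follow from the question. A father can hold parenting attitudes without having seen his child in the last month. The plan retains fathers without contact for behavior toward the child, where contact matters most, and drops them for attitudes.

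The fathers affected are plausibly central to the program. Protocol 1 (Program Summary) says that "the program does not plan on serving only fathers who are housed in treatment facilities, non-custodial, or justice involved", but that many participants are expected to have these characteristics. Lack of recent contact is likely to be more common among them, although the documents give no share.

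The missing wave adds a second problem. Par_Att is measured at entrance and exit. A contact filter at entrance defines a baseline subgroup. A filter at exit, or at both surveys, selects on something that happened after enrollment and that a fatherhood program may change. Fathers who gained or lost contact during the program would then enter or leave the paired sample depending on the rule chosen.

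**Working it through.** The text supplied gives no sample size, power or effect size for R1, so there is no planned figure to reproduce. The main check compares the passages.

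1. **Population asked about:** participating fathers with a child up to age 24 (Protocol 1.1, 1.2, 8.1). No contact condition.
2. **Study sample for attitudes:** consent plus both surveys (SAP, Identify study sample). No contact condition.
3. **Sample analysed for R1:** an eligible child and contact in the preceding month (SAP matrix).
4. **Retention rule:** parenting behavior only (SAP, Outcomes), so it does not undo step 3 for attitudes.
5. **Non-response analysis:** groups are defined by which surveys were completed, not by contact, so it would not show who the filter removed.
6. **Timing:** exit is in the last workshop session, about 4 weeks after enrollment (Protocol 9.3). A past-month question at exit therefore covers roughly the program period.

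Steps 1 to 4 establish the mismatch without arithmetic. The figures below are illustrations. The excluded share, the difference in change, the correlation and the number analysed are all assumed.

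**Numbers removed.** Planned intake is 63 + 4 × 125 = 563 fathers served. This is an upper reference, because study baseline collection was scheduled to close on 5/10/2024 and not all fathers complete both surveys. A no-contact share of 10%, 20%, 30% or 40% removes about 56, 113, 169 or 225.

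**Precision.** With equal SDs, excluding a share q multiplies the standard error by 1/√(1 − q). This gives 1/√0.8 = 1.118 and 1/√0.6 = 1.291, so it rises by 12% to 29% for q of 20% to 40%.

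**Shift from the narrower population.** The all-father mean change is (1 − q) × contact mean + q × no-contact mean, so the restricted estimate differs from it by q × difference. With a 0.2 SD difference this is 0.2 × 0.2 = 0.04 SD and 0.4 × 0.2 = 0.08 SD.

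**Selection if contact is judged at exit.** Let a share p have contact, and let latent contact correlate ρ with attitude change. With c = z(1 − p) and m = φ(c)/p, mean change among selected fathers shifts by ρm SD. If true mean change is zero and N fathers have both surveys before the filter, then n = Np, the SD in the selected group is √(1 − ρ²m(m − c)), s = ρm√n/SD, and the two-sided 5% test rejects with probability 1 − Φ(1.96 − s) + Φ(−1.96 − s).

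Example with p = 0.8, ρ = 0.2, N = 400: c = −0.842, m = 0.280/0.8 = 0.350, shift = 0.070, SD = √(1 − 0.04 × 0.417) = 0.992, n = 320, s = 0.070 × 17.89/0.992 = 1.26, rejection probability = 0.243.

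| Share with contact | Shift in SD, ρ = 0.1 / 0.2 | False-positive rate, N = 400 | False-positive rate, N = 200 |
|---|---|---|---|
| 90% | 0.019 / 0.039 | 7% / 12% | 6% / 8% |
| 80% | 0.035 / 0.070 | 10% / 24% | 7% / 15% |
| 70% | 0.050 / 0.099 | 13% / 39% | 9% / 22% |

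With ρ = 0 the shift is zero. If contact is judged at entrance, there is no post-baseline selection. In both cases the narrower population remains.

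**The case against.** The strongest objection is that the restriction may come from the instrument. Protocol 9.1 takes the attitude items from A3 of the fathers survey. They follow the contact items A2b and A2c, and the protocol describes them as frequency items. Such items might be asked only of fathers with recent contact. The SAP's remark that analytic samples vary with missing data would fit that, although its matrix gives these items an agreement scale. The survey's skip rules are not in the documents, so the point stays open. It decides which remedy applies. It does not remove the need to state the reason, the wave and the population.

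A reader might infer that the R1 result will be presented as holding for all participants. The documents do not say so. The restriction is disclosed in the sample column, and the Analytic approach section limits the tests to each outcome's analytic sample. What is shown is a mismatch between question and sample, not a planned misreport.

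A reader might also infer that the R1 estimate is biased. That requires contact to be judged at exit and to be related to attitude change, and neither is documented.

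Three further points stand in part. R1 is labelled exploratory in Protocol 1.2, and attitudes are secondary outcomes in the logic model (Protocol 3), although that section also calls the outcomes confirmatory. The comparison with financial and employment attitudes, which use all study participants, is weak because those measures are not about a child. The CONSORT diagram in Appendix C, which the SAP says shows exclusion criteria and anticipated size, is not in the text supplied and may give some of the missing numbers.

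**Conclusion.** The point holds as a mismatch between the question and the analysis sample. Following the SAP as written drops fathers without recent contact from R1, and nothing in the text supplied restores them. This rests on the documents alone.

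The selection concern is conditional. It applies if the filter uses the exit survey and contact is related to change. The wave is undefined, so the plan permits this. The precise term is post-baseline contact, since the exit question looks back over roughly the program period and not beyond it.

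The effect on the estimate cannot be derived. Under the assumptions shown, the shift from the narrower population alone is small (0.04–0.08 SD). Exit-based selection could raise a nominal 5% false-positive rate noticeably, for example to 10–24% at 80% contact, ρ of 0.1 to 0.2 and 400 fathers with both surveys. None of these figures describes this study. The correction should be made because it is cheap and lets R1 be answered for the group it names.

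**What to change.** In the Par_Att row of the SAP matrix, remove the contact condition. Analyse every consented father with a child up to age 24 whose composite can be scored at both entrance and exit under the plan's own item-removal and 20% missing-item rules. With all 7 items retained, one missing item is allowed (1/7 = 14%) and two are not (2/7 = 29%), so complete data on all 7 should not be required. Report the contact-restricted result as a sensitivity analysis, naming the wave used.

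If the survey did not ask these items of fathers without contact, say so. In that case define contact at entrance only, report the number excluded with their baseline characteristics, and restate R1's population as fathers in recent contact at entrance.

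The cost is one matrix cell or a short population statement, with no new data collection. Items that were not asked cannot be recovered. The SAP is dated 1/16/2025 and post-test collection was scheduled to end on 7/1/2024 (Protocol, Evaluation Timeline), so the change must be disclosed as made after data collection. The parenting-behavior row has the same cell, which conflicts with the retention rule for that outcome. That is a separate matter, but it can be reconciled in the same edit.

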1. RESEARCH QUESTIONS

1.1. OVERVIEW OF RESEARCH QUESTIONS

Please state the research question(s) that the evaluation intends to answer and for each research question indicate the type: implementation or outcome.

- *Implementation Questions: Identifying whether a program has been successful in attaining desired implementation goals (e.g., reaching intended target population, enrolling intended number of participants, delivering training and services in manner intended, etc.)*
- *Outcome Questions: Identifying whether program is associated with intended outcomes for participants (e.g., do participants' knowledge, attitudes, behaviors, or awareness change?)*

No	Research Question	Implementation or Outcome?
I1	To what extent were services offered and provided as intended?	Implementation
I2	To what extent is the Fresno Fatherhood curriculum and services offered to and completed by participants?	Implementation
I3	To what extent did the CQI Team carry out the steps in the CQI Plan each program year?	Implementation
R1	Will Fresno Fatherhood program participants experience significant increases in healthy parenting attitudes/beliefs/expectations after completing the Fresno Fatherhood program?	Outcome
R2	Will Fresno Fatherhood program participants experience significant increases in healthy parenting behaviors one year after program enrollment?	Outcome
R3	Will Fresno Fatherhood program participants experience significant increases in healthy co-parenting behaviors one year after program enrollment?	Outcome
R4	Will Fresno Fatherhood program participants experience significant increases in healthy employment attitudes/beliefs/expectations after completing the Fresno Fatherhood program?	Outcome

R5	Will Fresno Fatherhood program participants experience significant increases in healthy employment behaviors one year after program enrollment?	Outcome
R6	Will Fresno Fatherhood program participants experience significant increases in healthy financial attitudes/beliefs/expectations after completing the Fresno Fatherhood program?	Outcome
R7	Will Fresno Fatherhood program participants experience significant increases in healthy financial behaviors one year after program enrollment?	Outcome

* you may add rows by hitting the tab button, or right click and select insert row below

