R3	Interventions to be tested are the combination of the curriculum and services provided: 24/7 Dad curriculum, Job Readiness and Post-Employment support	Community fathers (ages 18 and older), who have children ages 24 and younger and reside in communities with high rates of poverty.	Pre-intervention responses will be compared with responses collected 1-year post-enrollment (follow up).	We expect that program participants will experience a significant increase in healthy co-parenting behaviors one year after program participation.	Exploratory
R4	Interventions to be tested are the combination of the curriculum and services provided: 24/7 Dad curriculum, Job Readiness	Community fathers (ages 18 and older), who have children ages 24 and younger and reside in communities with high	Pre-intervention responses will be compared with responses collected immediately following program completion(post-intervention).	We expect that program participants will experience a significant increase in healthy employment attitudes/beliefs/expectations after completing the Fresno Fatherhood program.	Exploratory

	and Post-Employment support	rates of poverty.			
R5	Interventions to be tested are the combination of the curriculum and services provided: 24/7 Dad curriculum, Job Readiness and Post-Employment support	Community fathers (ages 18 and older), who have children ages 24 and younger and reside in communities with high rates of poverty.	Pre-intervention responses will be compared with responses collected 1-year post-enrollment (follow up).	We expect that program participants will experience a significant increase in healthy employment behaviors one year after program participation.	Exploratory
R6	Interventions to be tested are the combination of the curriculum and services provided: 24/7 Dad curriculum, Job Readiness and Post-Employment support	Community fathers (ages 18 and older), who have children ages 24 and younger and reside in communities with high rates of poverty.	Pre-intervention responses will be compared with responses collected immediately following program completion (post-intervention).	We expect that program participants will experience a significant increase in healthy financial attitudes/beliefs/expectations after completing the Fresno Fatherhood program.	Exploratory

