- **Goal 3 – Provide job readiness/placement and other supportive follow up services as secondary services to participants:** Candidates who receive job readiness/placement and other support services will understand that they will receive services that will help them obtain and maintain ongoing employment. The ongoing follow up support is important to

ensure that participants will increase their ability to financially provide for their children and families.

- **Goal 4 - Conduct Continuous Quality Improvement (CQI) to ensure full implementation of RISE services to both study groups:** Reports prepared and presented to the CQI Team by evaluators will use a series of performance indicators to track key outputs over time to identify any Fresno Fatherhood services that is delivered to participants that might fall short of the intended amounts to be offered (i.e., fidelity standards) and received (i.e., dosage thresholds). The CQI Team will then work with project staff to develop and implement performance interventions to address any outputs that need improvement to ensure the services offered to and received by participants meet the intended amounts by the end of each program year.

Desired Outcomes: Outcomes specified in the logic model theorize the primary and secondary outcomes that are desired for participants in each study group after they receive Fresno Fatherhood *primary and secondary services*. Secondary outcomes are the improved attitudes and expectations that indicate and reflect participant engagement in parenting, co-parenting, and financial stability. Primary outcomes are the healthy behaviors exhibited by participants for parenting, co-parenting, and economic stability that ultimately define the benefits of Fresno Fatherhood program participation. Outcomes specified in the logic model are confirmatory since it is expected that participation in the Fresno Fatherhood curriculum will result in positive increases in primary and secondary outcomes related to parenting, co-parenting, and financial stability.

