#### **Analytic approach**

The main goal of this descriptive study is to assess pre-to-post change scores in the attitudinal outcomes listed above, and assess pre-to-one-year follow-up change scores in the behavioral outcomes listed above among program participants before and after primary workshops. We will use paired sample t-tests to assess the magnitude and significance of changes among program participants in the analytic sample for each outcome. For binary economic stability outcomes, we will descriptively report the percent of participants who opened a checking or savings account 1 year after enrollment, compared to the percent who had opened these accounts before the program. For binary employment outcomes, we will descriptively report the percent of participants who did not have a resume 1 year after enrollment, compared to the percent who did not have a resume before the program. We will adjust our p-values for multiple hypothesis testing and report the adjusted p-values in the appendix of the final report.

For the implementation analysis, program fidelity will be descriptively reported by the percentage of enrolled participants who receive: 1) any primary workshops, 2) employment supports, 3) substantive service contacts, 4) referrals. The program aims to provide all participants each of these four program components, so the percentage of participants who receive each of these will be compared to the 100% benchmark. Number of substantive service contacts per participant will also be compared to the benchmark of 8 SSCs set by OFA for FIRE grantees.

Exploratory analysis will examine how dosage varies by workshop characteristics (e.g., timing and length of sessions) and participant characteristics (e.g., age, employment status, relationship status).

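### Employment behavior (R5) is analysed only in fathers with no resume at entrance, so the before figure is 100% by construction and no decline can appear

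*SAP*

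**What the plan says.** In the SAP, Defining analysis measures, the sample for Emp_Beh (a 0/1 measure of having a completed resume, from the nFORM entrance survey and the OLLE 1-year follow-up) is "All study participants who came into the program without a resume". The same section states: "For standalone survey items, a change score will be calculated" from each participant's pre and post answers.

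The Analytic approach section plans this descriptive comparison: "percent of participants who did not have a resume 1 year after enrollment, compared to the percent who did not have a resume". The second percentage is the one at program entry. The section neither repeats nor lifts the restriction.

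The SAP's study sample section already defines who enters a behavioral analysis: consenting participants with an entrance and a follow-up survey. The other binary outcome, Fin_Beh, is limited to fathers with a child aged 24 or younger, not by whether they already held an account.

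Protocol 1.1 words R5 as "Will Fresno Fatherhood program participants experience significant increases in healthy employment behaviors one year after program enrollment". On whether the study population differs from those served, Protocol 8.1 answers: "No difference, all program participants will be study participants".

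**The concern.** The sample is selected on the baseline value of its own outcome. The share of fathers without a resume who have one a year later is a sound uptake figure for that subgroup. Shown as a before/after change, it looks like a result for the program's participants, and it cannot turn out badly. Protocol 9.1 lists only this one item for employment behavior, so no other analysis covers fathers who arrived with a resume.

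The interpretation adds to the problem. Protocol 5 treats the R5 pre-to-follow-up change as the maximum benefit attributable to services. Protocol 1.2 labels R5 exploratory, but Protocol 3 states "Primary outcomes are the healthy behaviors exhibited by participants" and calls the logic-model outcomes confirmatory. A measure that can only be zero or favourable is a weak basis for either use.

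If the Analytic approach sentence is instead meant to cover all participants, it conflicts with the sample in the measure table. The text is ambiguous on this, and either reading needs an edit.

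**Working it through.** **What follows from the text alone.** Code Emp_Beh as 1 for having a resume and 0 for not. The restriction sets the entrance value to 0 for everyone analysed. Then:
- percent without a resume before = 100%, for any data;
- change = follow-up value − 0, which is 0 or +1;
- percent without a resume at 1 year is at most 100%.

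No assumption is needed for this. There is no planned figure for R5 in the documents to reproduce.

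**Illustrating the size.** The inputs below are assumed, because the documents give no resume prevalence or switching rates. Let p = share with a resume at entrance, g = share of those without one who gain one, and l = share of those with one who lose it.
- All participants, with a resume at 1 year = p(1 − l) + (1 − p)g.
- SAP sample, without a resume at 1 year = 1 − g.

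| Case | p | g | l | All participants, with a resume | SAP sample, without a resume |
|---|---|---|---|---|---|
| No loss | 0.5 | 0.10 | 0 | 50% → 0.50 + 0.05 = 55% | 100% → 90% |
| Equal switching | 0.5 | 0.10 | 0.10 | 50% → 0.45 + 0.05 = 50% | 100% → 90% |
| Equal switching | 0.5 | 0.20 | 0.20 | 50% → 0.40 + 0.10 = 50% | 100% → 80% |
| More loss than gain | 0.3 | 0.10 | 0.20 | 30% → 0.24 + 0.07 = 31% | 100% → 90% |
| More loss than gain | 0.5 | 0.10 | 0.20 | 50% → 0.40 + 0.05 = 45% | 100% → 90% |
| More loss than gain | 0.7 | 0.10 | 0.20 | 70% → 0.56 + 0.03 = 59% | 100% → 90% |

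With g = 0.10, the SAP figure is the same 10-point improvement whether all participants gain 5 points, stay level or lose 11.

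**Answer error with no true change.** Let q = true share without a resume, and e = an independent error rate at each survey. In the SAP sample the percent without a resume at 1 year is [q(1 − e)² + (1 − q)e²] / [q(1 − e) + (1 − q)e].
- q = 0.3, e = 0.05: (0.27075 + 0.00175)/(0.285 + 0.035) = 0.2725/0.32 = 85.2%.
- q = 0.5, e = 0.05: 1 − 2(0.05)(0.95) = 90.5%.
- q = 0.5, e = 0.10: 1 − 2(0.10)(0.90) = 82.0%.
- q = 0.7, e = 0.05: (0.63175 + 0.00075)/(0.665 + 0.015) = 0.6325/0.68 = 93.0%.

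In the full sample the reported percentage is the same at both surveys, because errors in the two directions balance over time. In the SAP sample they appear as improvement.

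**If the outcome were tested.** The Analytic approach section opens with paired t-tests for each outcome, then describes the binary outcomes as descriptive reports. If the t-test were applied here, with k gains among n fathers and no losses possible, t = √[k(n − 1)/(n − k)]. For k = 4 this gives t = 2.06 at n = 50, 2.03 at n = 100 and 2.02 at n = 200, each with p < 0.05. Four gains would be enough at any of these sizes.

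**The case against.** The best defence is that nothing is hidden. The restriction is stated in the Sample column, the outcome is reported descriptively, and R5 is labelled exploratory. A careful reader would see that 100% is simply where the subgroup starts, and that a fall to 90% means 10% gained a resume. On a yes/no item only fathers without a resume can improve, and R5 asks about increases. If a completed resume is rarely lost, the restriction changes the size of the result but not its direction. The natural reading may also be that the two SAP sections agree, since the text says participants rather than all participants.

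Much of this stands. It limits the severity, makes the conflict between sections conditional, and is why a no-loss case appears above. It does not remove the defect. Even with no losses, the change in the subgroup is g while the change among all participants is (1 − p)g, so at p = 0.5 the reported gain is twice that for participants as a whole. Loss cannot be ruled out: Protocol 9.1 describes the item as an updated resume, and a resume can go out of date within a year. The SAP's other outcome-specific samples, such as having seen the child in the past month, are not chosen on the outcome's own baseline value. Appendix C, which the SAP cites for exclusions, is not in the text available. It might explain the restriction, but it could not make the before figure informative.

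**Conclusion.** The concern holds. As the SAP's measure table is written, the before half of the R5 comparison is fixed at 100%, an unfavourable change is impossible, and the result describes a subgroup instead of the program participants named in R5. That conclusion rests only on the SAP's definitions. The percentages rest on assumed prevalence, switching and error rates, and show that the SAP figure can improve by 10 points while the full sample worsens by 5 (p = 0.5, g = 0.10, l = 0.20). Because the planned report is descriptive, the main harm is a misleading display. A false claim of significance would follow only if the general t-test sentence were applied to this outcome. This should be corrected before the final analysis.

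**What to change.** 1. In the measure table, change the Emp_Beh sample to all study participants with both an entrance and a 1-year answer to the resume item.
2. In Analytic approach, report for those same fathers the percent with a resume at each time, the counts moving from no to yes and from yes to no, and the paired difference with a 95% CI. If a test is wanted, use McNemar's test.
3. Keep the percent who gained a resume among fathers without one at entrance as a labelled supplementary figure, with no before/after comparison.
4. Use one description of the item, updated or completed, in both documents.

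If the sponsor prefers to keep the restricted sample, the minimum is to drop the before comparison, call the result the proportion gaining a resume, and state that R5 is answered only for that subgroup.

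The cost is one table cell and one sentence, plus the wording alignment. Protocol 9.1 lists the item at entrance and follow-up, so new data should not be needed. The follow-up form is not shown, however, and the sponsor should confirm that the item is not skipped for fathers who had a resume at entrance. The SAP is dated 1/16/2025 and the protocol timeline runs follow-up to 5/31/2025, so any skip should be checked promptly, as missed answers may not be recoverable. The reported gain will probably look smaller.
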